8.2.3.5 End of study

- Visit date
- Discontinuation or continuation (if interruption, date of last administration, reason for interruption)
- The final efficacy evaluation
- NIS physician's electronic signature for data integrity

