8.3.2.2 Endpoints of effectiveness

8.3.2.2.1 Main endpoint

Change from baseline in HbA1c after 12 weeks and/or 24 weeks of treatment

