8.3.2.2.2 Other endpoints

- Occurrence of treat to target effectiveness response that is an HbA1c under treatment of < 7% after 12 weeks and/or 24 weeks of treatment
- Occurrence of relative effectiveness response (HbA1c lowering by at least 0.5% after 12 weeks and/or 24 weeks)
- Change from baseline in fasting plasma glucose (FPG) after 12 weeks and/or 24 weeks of treatment
- Change from baseline in body weight after 12 weeks and/or 24 weeks of treatment.
- Change from baseline in blood pressure (SBP, DBP) after 12 weeks and/or 24 weeks of treatment.

Proprietary confidential information © 2017 Boehringer Ingelheim International GmbH or one or more of its affiliated companies

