8.7.3 Efficacy analysis

- Mean, standard deviation, minimum value, maximum value, and median of changes in glycosylated hemoglobin(HbA1c) and fasting plasma glucose(FPG), body weight, and blood pressure (SBP, DBP), which were measured at the last visit versus baseline, should be presented, and if there is difference before administration versus after administration should be analyzed using paired t-test.
- ② If there is difference in the change of glycosylated hemoglobin(HbA1c) according to demographic parameters mentioned in 8.7.1 should be analyzed using t-test or ANOVA(Analysis of Variance).
- The frequency and percentage of patients who had glycosylated hemoglobin(HbA1c) reaching less than 7% (target efficacy response rate) at the last visit should be calculated, and the frequency and percentage of patients with glycosylated hemoglobin(HbA1c) decreased by at least 0.5% at the last visit should be calculated.
- For final efficacy evaluation (improved, unchanged, aggravated, unassessable) and 'effective(improved)'/'ineffective(unchanged, aggravated)', the number and percentage of subjects should be mentioned. The final effectiveness evaluation of "Improved" will be classified as "Effective", "Unchanged" and "Aggravated" will be classified as "Ineffective". The effectiveness rate and its 95% confidence intervals will be estimated with exact method.
- ⑤ To estimate any factors that are thought to influence an effective ratio, logistic regression analysis should be conducted, and for statistically significant parameters, the meaning should be described.

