8.7.5 Handling of missing data

Maximum attempt will be made to ensure the completeness of data collection. All available data will be used in the data analysis.

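### The HbA1c change and the <7% response are defined on treatment, but section 8.7.3 analyses the last-visit value with no condition on drug status, so values taken after JARDIANCE was stopped can enter both

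*Protocol*

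**What the plan says.** **Endpoints (8.3.2.2).** The main effectiveness endpoint is "Change from baseline in HbA1c after 12 weeks and/or 24 weeks of treatment". The target response is "an HbA1c under treatment of < 7% after 12 weeks and/or 24 weeks of treatment". The relative response is worded differently, as "HbA1c lowering by at least 0.5% after 12 weeks and/or 24 weeks", with no reference to treatment.

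**Analysis (8.7.3).** Changes in HbA1c and the other measures are those "which were measured at the last visit versus baseline, should be presented". The target rate counts patients with HbA1c "reaching less than 7% (target efficacy response rate) at the last visit should be calculated". The rate of falls of at least 0.5% is also taken at the last visit. None of these carries a condition on still taking JARDIANCE.

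**Who and what is included.** The efficacy set (8.3.1.4) requires consent, attendance on schedule, having taken the drug and an efficacy assessment. Its exclusions are exclusion from the safety set and missing efficacy information. Stopping the drug is not among them. Section 8.7.5 adds: "All available data will be used in the data analysis".

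**What is recorded.** Visits 2 and 3 are timed from Visit 1 (8.2.3.3, 8.2.3.4). Each records HbA1c together with any change in JARDIANCE, including a discontinuation date. The end-of-study form (8.2.3.5) records "Discontinuation or continuation (if interruption, date of last administration, reason for interruption".

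**The concern.** The endpoint section asks what HbA1c does while patients take the drug. The analysis section answers with whatever was measured last. A patient who stops JARDIANCE at week 6 and attends the week-12 visit has the stop date and an HbA1c entered at the same visit. That value is six weeks off drug. Under 8.3.1.4, 8.7.3 and 8.7.5 read literally, it is kept in the mean change and in a response rate defined as under treatment.

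Two different quantities are at stake: the effect while on the drug, and the course of all patients who started it, whatever happened next. Either is a legitimate summary in a routine-practice study. The protocol defines the first and specifies an analysis that can deliver the second. A reader of the final report could not tell which one a figure represents, or how many patients were off drug when it was measured. Effectiveness is a secondary objective (7.2), but this affects its main endpoint.

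**Working it through.** **Step 1: the text side by side.** There is no figure to reproduce. The 3,000 patients are a regulatory requirement (8.5), and the protocol states no discontinuation rate or expected response rate.

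| Measure | Endpoint wording (8.3.2.2) | Analysis (8.7.3) | Conflict in wording? |
|---|---|---|---|
| HbA1c change | after 12 and/or 24 weeks, of treatment | last visit against baseline | yes |
| HbA1c <7% | under treatment, and of treatment | last visit | yes |
| HbA1c fall of at least 0.5% | after 12 and/or 24 weeks only | last visit | no, only the practical issue |

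**Step 2: does another section restore the condition?** The efficacy set does not, the missing-data section does not, and visit timing runs from Visit 1 rather than by exposure. Section 8.2 calls follow-up a treatment period, and 8.3.3.2 asks for HbA1c after 12 and 24 weeks of treatment. These show intent but give no rule for a value measured after stopping.

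**Step 3: illustration for the mean change.** All inputs are assumed. Let d be the share of the efficacy set off drug at the last HbA1c, and let the on-drug change be -0.70.

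Reported change = (1 - d) x (-0.70) + d x (off-drug change)

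| d | Off-drug change 0 (back to baseline) | Off-drug change -1.0 (another effective agent) |
|---|---|---|
| 5% | 0.95 x -0.70 = -0.665 | -0.665 - 0.05 = -0.715 |
| 10% | 0.90 x -0.70 = -0.63 | -0.63 - 0.10 = -0.73 |
| 20% | 0.80 x -0.70 = -0.56 | -0.56 - 0.20 = -0.76 |

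**Step 4: illustration for the <7% rate.** Assume 40% response on drug and all 3,000 patients evaluable.

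Reported rate = (1 - d) x 40% + d x (off-drug rate); 95% half-width = 1.96 x sqrt(p(1 - p)/3000)

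| d (patients) | Off-drug rate 15% | Off-drug rate 40% | Off-drug rate 60% |
|---|---|---|---|
| 5% (150) | 38.75% (-1.25 points) | 40% (0) | 41.0% (+1.0) |
| 10% (300) | 37.5% (-2.5) | 40% (0) | 42.0% (+2.0) |
| 20% (600) | 35.0% (-5.0) | 40% (0) | 44.0% (+4.0) |

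The half-width is 1.71 to 1.78 points throughout. At d = 5% the shift lies inside it. At 10% or more it lies outside in both scenarios where the off-drug rate differs from the on-drug rate. With fewer than 3,000 evaluable patients the half-width would be larger.

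**The case against.** The strongest reply is that the protocol never says off-drug values count. Sections 8.2 and 8.3.3.2 tie follow-up and measurement to treatment, so the last visit can be read as the last on-treatment visit. Other passages can be read as treating discontinuation as the end of observation: 8.9.1 speaks of censoring due to discontinuation, 8.2.3.6 pairs early discontinuation with the final visit, and 10.2 ends adverse event collection 30 days after the last dose. Nowhere does the protocol say that patients who stop attend later effectiveness visits. A detailed rule may also sit in the SAP, which is not available here.

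Part of this stands. A reader might infer that off-drug values do count as JARDIANCE response; the documents support only that they can. But the point does not need patients to continue to later visits, because a stop date and an HbA1c can be recorded at one and the same visit. A rule in the SAP would settle the practice but would leave the protocol's endpoint and analysis sections in disagreement.

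A reader might also infer that drug exposure is ignored altogether. It is not. Section 8.7.1 lists total period of use, reason for early interruption and use beyond 24 weeks, and 8.7.3 tests the HbA1c change by the 8.7.1 parameters. That is a subgroup comparison and leaves the headline mean and response rates as they are.

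Finally, on-treatment values are not simply the better estimate. They select patients who tolerated the drug, and a routine-practice study may reasonably summarise everyone. This stands, and is why both results belong in the report.

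**Conclusion.** The concern holds as a conflict between 8.3.2.2 and 8.7.3 for two results, the main HbA1c change and the <7% rate. The rate of falls of at least 0.5% shares the practical problem but contradicts nothing in its own definition.

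Neither size nor direction can be established. With an assumed 5-20% off drug and fully back at baseline, an assumed fall of 0.70 points would be reported as 0.67 to 0.56. With an assumed fall of 1.0 on a replacement agent it would be reported as 0.72 to 0.76. A reader might infer that the analysis must understate the effect; the documents do not support that, since they give neither a discontinuation rate nor what follows discontinuation. The matter should be corrected because it touches the main effectiveness endpoint and costs little.

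**What to change.** In 8.7.3, use the stop dates collected at Visits 2 and 3 and at end of study to flag each effectiveness value as on or off JARDIANCE. The exact definition of the flag, such as how soon after the last dose a value counts as off drug, can be fixed in the SAP before the data are analysed. Report the HbA1c change and the <7% rate for on-treatment values, as the endpoints define them, beside the last-visit result using all values. Give the number of patients off drug at each visit. Then align 8.3.2.2 with 8.7.3 so that each result states which quantity it estimates.

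The cost is a few sentences and one derived variable, with no new data. The downside is that the on-treatment figure rests on somewhat fewer patients and favours those who tolerated the drug, so it should not be shown without the all-values figure.

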8.2.1 Study sites

A total of 3,000 patients will be enrolled at approximately 70 sites by as many as 70 or more NIS physicians. To minimize the selection bias at the site level, the goal is to have participating centers reflect a balance between general hospitals and clinics for surveillance. The treating physicians will mainly be internists. To minimize the selection bias, consecutive patients from each site who meet inclusion criteria will be enrolled in this study.

As provided in the "Standards for Re-examination of New Drugs of the Ministry of Food and Drug Safety Notification, BI OPU should select study site according to the following requirements;

- Equipment/facility, and manpower capable of fully achieving the goal of investigation should be held;
- The investigator should have specialized knowledge of the drug subject to investigation and the indication, have completed education/training necessary for performing the investigation, or have practical experience;
- 3 Study site and the investigator should strictly keep confidential the record of subject's personal data
- ① The investigator should be fully aware of the 『Standards for Re-examination of New』 and study protocol.

Proprietary confidential information © 2017 Boehringer Ingelheim International GmbH or one or more of its affiliated companies

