8.2.2 Study population

8.2.2.1 Main diagnosis for study entry

Patients diagnosed with T2DM will be included.

8.2.2.2 Inclusion criteria:

- Patients who have started at first time on JARDIANCE[®] in accordance with the approved label in Korea
- Age ≥19 years at enrolment
- Patients who have signed on the data release consent form

8.2.2.3 Exclusion criteria:

- Known hypersensitivity to empagliflozin or any of its excipients
- Patients with type 1 diabetes or for the treatment of diabetic ketoacidosis (DKA)
- Patients with persistent eGFR<60 mL/min/1.73 m², end stage renal disease or on dialysis
- Patients with rare hereditary conditions of galactose intolerance, the Lapp lactase deficiency or glucose-galactosemalabsorption
- Patients for whom empagliflozin is contraindicated according local label of JARDIANCE[®]

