8.3.1.4 Number of cases subject to efficacy evaluation

These cases include those who signed the informed consent form to participate in this study as subject, visited as per the study schedule, took JARDIANCE[®], and were evaluated for the efficacy.

Reflecting Ministry of Food & Drug Safety (MFDS) guideline, the cases below shall be excluded from efficacy analysis (defined below) set in the following order:

- a. Patients excluded from safety analysis set listed in section 8.3.1.3
- b. Patients with missing information of assessment of efficacy set listed in section 8.3.2.2 at visit 2, visit 3.

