8.3.3.2 Assessment of efficacy

① HbA1c:

HbA1c should be collected within 1 month prior to baseline and after 12 weeks and 24 weeks of treatment.

② Fasting Plasma Glucose (FPG):

FPG should be collected within 1 month prior to baseline and after 12 weeks and 24 weeks of treatment.

3 Body Weight:

Body weight should be collected within 1 month prior to baseline and after 12 weeks and 24 weeks of treatment.

Blood Pressure (SBP, DBP):

Blood pressure(SBP, DBP) should be collected within 1 month prior to baseline and after 12 weeks and 24 weeks of treatment.

S Final efficacy evaluation: Final efficacy evaluation should be accessed and recorded at the end of the last visit.

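### The HbA1c <7% target response rate has no baseline condition, so patients who start and stay below 7% are counted as responders

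*Protocol*

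**What the plan says.** Section 8.3.2.2.2 lists, among the other effectiveness endpoints, occurrence of a "treat to target effectiveness response that is an HbA1c under treatment of < 7" per cent, after 12 and/or 24 weeks. Section 8.7.3 turns this into the frequency and percentage of patients with HbA1c "reaching less than 7% (target efficacy response rate) at the last visit should be calculated". The same item also asks for the percentage whose HbA1c fell by at least 0.5% at the last visit.

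Entry is broad. Section 8.2.2.1 says "Patients diagnosed with T2DM will be included". Section 8.2.2.2 asks for first use of the drug "in accordance with the approved label in Korea", age 19 or over, and consent. None of the exclusion criteria in 8.2.2.3 mentions HbA1c. Section 8.2.1 says "consecutive patients from each site who meet inclusion criteria will be enrolled in this study".

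The efficacy set in 8.3.1.4 drops patients already excluded from the safety set and "Patients with missing information of assessment of efficacy set listed in section 8.3.2.2 at visit 2, visit 3". It has no rule on the baseline HbA1c level. Baseline HbA1c itself is planned data: section 8.3.3.2 says "HbA1c should be collected within 1 month prior to baseline and after 12 weeks and 24 weeks of treatment".

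**The concern.** The target response is defined only by where a patient ends, not by where the patient began. Sections 8.1.3 and 8.2.3.2 allow other medication and record anti-hyperglycemic agents taken in the month before baseline, so patients already controlled on other agents can enter. Someone at 6.6% before the first dose and 6.6% at the last visit would be recorded as a target response although nothing changed.

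This is a single-arm study (8.1), so each patient's baseline is the only reference for effectiveness. A responder rate that ignores baseline gives up that reference and moves with the mix of patients enrolled. The planned subgroup analyses do not undo the mixing: they concern HbA1c change rather than this rate, and the parameters in 8.7.1 that they use do not include baseline HbA1c.

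**Working it through.** The protocol states no expected target rate and no baseline HbA1c distribution, so there is no figure of its own to reproduce.

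**Does any rule remove patients who start below 7%?**

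- Endpoint definition (8.3.2.2.2): on-treatment value only.
- Analysis (8.7.3): last-visit value only.
- Inclusion and exclusion criteria (8.2.2.2, 8.2.2.3): no HbA1c limit.
- Enrolment (8.2.1): consecutive eligible patients, so the baseline mix is whatever practice supplies.
- Efficacy set (8.3.1.4): exclusions for safety-set reasons and missing efficacy data only.

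None does.

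**Size, as an identity.** Let b be the share with baseline HbA1c <7%, s the share of those still <7% at the last visit, and r the rate among patients with baseline ≥7%.

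- Planned rate = b × s + (1 − b) × r
- Excess over r = b × (s − r)

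The excess is positive whenever s is larger than r.

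**Illustration, with assumed s = 85% and r = 30%:**

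| b (assumed) | Planned rate | Excess over 30% | Share of counted responders already <7% at baseline |
|---|---|---|---|
| 0% | 30.0% | 0 points | 0% |
| 10% | 8.5 + 27.0 = 35.5% | 5.5 points | 8.5 / 35.5 = 24% |
| 20% | 17.0 + 24.0 = 41.0% | 11.0 points | 17.0 / 41.0 = 41% |
| 30% | 25.5 + 21.0 = 46.5% | 16.5 points | 25.5 / 46.5 = 55% |

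**Second illustration.** Baseline and last-visit HbA1c were simulated as bivariate normal. The assumed inputs were baseline mean 7.5 to 8.5%, SD 1.0 to 1.3, correlation 0.7, and a mean fall of 0, 0.5 or 0.85 points. The value 0.85 is borrowed, for scale only, from the largest placebo-corrected reduction quoted in section 6.2.

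| Mean | SD | Fall | b | Planned rate | Rate among baseline ≥7% | Excess |
|---|---|---|---|---|---|---|
| 8.5 | 1.0 | 0.5 | 6.7% | 15.8% | 12.1% | 3.7 points |
| 8.0 | 1.0 | 0.5 | 15.9% | 30.9% | 22.3% | 8.6 points |
| 7.5 | 1.3 | 0.5 | 35.0% | 50.1% | 32.7% | 17.4 points |

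The first and last rows are the smallest and largest excess over all the settings with a fall of 0.5 or 0.85. With a fall of zero, the planned rate is still 6.7% to 35.0%, set entirely by the assumed baseline distribution.

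**The case against.** The strongest reply is that the rate measures what it is defined to measure, the share at target on treatment. Section 8.3.2.2.3 also counts maintenance of disease factors as improvement, so counting patients who stay at target is consistent with the rest of the plan. This stands in part: the percentage is a legitimate description. What it does not support is the label of a response rate, because that label covers patients who had no distance to travel.

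A second reply is that 8.7.3 names no denominator, that reaching a level may imply having started above it, and that a statistical analysis plan may settle this. But 8.3.2.2.2 defines the endpoint by the on-treatment value alone. The definition is therefore fixed in the protocol, not left open, and as written it includes these patients. The label might limit who starts the drug, but the protocol reproduces no HbA1c limit from it.

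A third reply is that the main effectiveness endpoint, HbA1c change, and the fall of at least 0.5% are both relative to baseline and sit beside this rate. That is true and limits the harm, but it does not repair this rate.

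A reader might infer more than the documents support:

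- **That the rate does not measure response at all, or mainly reflects who was enrolled.** In the first illustration, patients already below 7% supply more than half of the counted responders only at b = 30%.
- **That the flaw is what prevents reading the rate as a drug effect.** No single-arm proportion isolates a drug effect. In the simulation with zero fall, the rate restricted to baseline ≥7% is still 4.2% to 18.1%.
- **That the 0.5% response needs the same repair.** It is already relative to baseline, and no defect in it has been shown.

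**Conclusion.** The point holds as a matter of definition. Followed as written, the target response rate counts patients who start and stay below 7%, and so mixes baseline control with response. It overstates the rate among patients who could respond by b × (s − r).

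The size cannot be derived from the protocol. The figures of 5.5 to 16.5 points, and about 4 to 17 points in the simulation, rest wholly on the assumed inputs, and the excess vanishes if nobody starts below 7%. No rule in the protocol ensures that.

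The consequence is modest. This is one of the other endpoints under a secondary objective, in a study whose primary objective is safety, and 8.7.3 plans no test or confidence interval for it. It is worth correcting because the correction is cheap, not because the study's conclusions depend on it.

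**What to change.** In 8.3.2.2.2 and 8.7.3:

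1. Calculate the target response rate among patients with baseline HbA1c of 7.0% or more, and state the denominator. A patient at exactly 7.0% belongs in this group, since the target is strictly below 7%. Show how many patients have no baseline HbA1c and so fall in neither group.
2. Report separately the share of patients with baseline HbA1c below 7% who remain below 7%.
3. Keep the all-patient proportion below 7%, shown at baseline and at the last visit, as a description only.

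No new data are needed, because baseline HbA1c is already collected. The cost is a smaller denominator and a lower reported rate. The loss of precision is small. If all 3,000 patients were evaluable and 30% started below 7%, 2,100 would remain. At a rate of 30%, the 95% half-width would be 1.96 × √(0.30 × 0.70 / 2,100) = 1.96 points, against 1.96 × √(0.30 × 0.70 / 3,000) = 1.64 points with all 3,000.

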8.3.2.2.3 The final efficacy evaluation

Records by performing the final efficacy evaluation at the end of the last visit

- ① Improved: If determined as there is any effect of maintaining or improving disease related factors.
- ② Unchanged: If disease related factors have not been changed compared with before administration, and not determined as there is any effect of maintaining symptoms.
- 3 Aggravated: If disease related factors are worse than before administration.
- 4 Unassessable: If it cannot be determined due to insufficient information collected. (Even though there are any objective indicators present, it is possible to belong to this grade.)

'Improved' is assessed as "Effective", "Unchanged" and "Aggravated "are assessed as "Invalid".

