8.5 STUDY SIZE

The sample size of 3,000 patients is based on the requirement of the local regulatory authority (MFDS). As per regulation, long-term surveillance is necessary for the T2DM indication. Since T2DM is chronic disease it might be restrictive to collect safety and effectiveness data in short-term (12weeks) period, all patients will be enrolled for long-term (24weeks) surveillance.

Proprietary confidential information © 2017 Boehringer Ingelheim International GmbH or one or more of its affiliated companies

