8.7.2 Safety analysis

- ① Among the subjects of safety evaluation, the number of subjects with adverse event incurred and the number of adverse events incurred should be calculated, and the incidence rate of adverse events and the 95% confidence interval should be presented.
- ② The number and percentage of adverse events by type and category should be presented.
- 3 Analysis should be made using Chi-square test or Fisher's Exact test on the adverse event onset status by demographic data of subjects of safety evaluation.

Proprietary confidential information © 2017 Boehringer Ingelheim International GmbH or one or more of its affiliated companies

④ To estimate any factors that are thought to influence the analyzed incidence rate of adverse events, logistic regression analysis should be conducted, and for statistically significant parameters, the meaning should be described.

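### The exact 95% CI fixed for the effectiveness rate ignores possible within-site correlation of a physician-rated outcome, so add a site-clustered interval

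*Protocol*

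**What the plan says.** Section 8.2.1 gives the sampling structure: "A total of 3,000 patients will be enrolled at approximately 70 sites by as many as 70 or more NIS physicians". Within a site, "consecutive patients from each site who meet inclusion criteria will be enrolled in this study". The section also aims for a balance of general hospitals and clinics.

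Section 8.3.2.2.3 defines the outcome behind the effectiveness rate. At the end of the last visit each patient is rated improved, unchanged, aggravated or unassessable. The top category reads "Improved: If determined as there is any effect of maintaining or improving disease related factors". No cut-off for HbA1c or any other measure is attached, and a patient may be rated unassessable even when objective indicators exist. Improved counts as effective; unchanged and aggravated do not.

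Section 8.7.3 then fixes the interval method: "The effectiveness rate and its 95% confidence intervals will be estimated with exact method". No section mentions site or physician clustering, and the limitations in section 8.9 cover only loss to follow-up, channeling and confounding.

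Elsewhere the protocol is less specific. For adverse events, section 8.7.2 asks that "the incidence rate of adverse events and the 95% confidence interval should be presented", without naming a method. Logistic regression is named in sections 8.7.2 and 8.7.3 without covariates, site term or variance estimator.

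**The concern.** An exact binomial interval takes its width from the number of patients alone, as if each rating were a separate draw. Here about 43 patients at a site are rated by one physician or a few. The category wording leaves room for physicians to differ in what they call improved, and case mix may differ between hospitals and clinics. Both would make ratings within a site more alike than ratings from different sites.

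The study has a single arm, and section 8.5 sets the sample size by regulatory requirement, not from a precision target. The rates and their intervals are therefore the main statistical output. If the interval for the effectiveness rate is too narrow, the report claims more precision about Korean practice than the sampling provides.

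**Working it through.** The protocol states no numerical interval, expected rate or precision target, so there is no figure of its own to reproduce.

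**Inputs from the protocol.** N = 3,000 and about 70 sites (section 8.2.1); exact 95% CI (section 8.7.3).

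**Assumptions, not in the protocol.** ICC from 0.001 to 0.10; effectiveness rate 80%, for illustration; equal site sizes at first.

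**Step 1, site size.** m = 3,000 / 70 = 42.86.

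**Step 2, design effect.** DE = 1 + (m - 1) x ICC = 1 + 41.86 x ICC. Effective sample size = 3,000 / DE. The interval should be wider by about sqrt(DE). Approximate coverage of the unadjusted interval = 2 x Phi(1.96 / sqrt(DE)) - 1.

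Example, ICC 0.05: DE = 1 + 41.86 x 0.05 = 3.09; effective n = 3,000 / 3.09 = 970 (unrounded DE); sqrt(3.09) = 1.76.

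**Step 3, check by simulation.** Beta-binomial data, 70 sites of 42 or 43 patients (3,000 in total), true rate 80%, 20,000 replicates, coverage of the nominal 95% exact interval.

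| ICC (assumed) | DE | Effective n | Width factor | Coverage, formula | Coverage, simulated | Exact 95% CI at 80%, using effective n |
|---|---|---|---|---|---|---|
| 0 | 1.00 | 3,000 | 1.00 | 95.0% | 95.3% | 78.5-81.4% |
| 0.001 | 1.04 | 2,879 | 1.02 | 94.5% | not run | not run |
| 0.01 | 1.42 | 2,115 | 1.19 | 90.0% | 90.2% | 78.2-81.7% |
| 0.05 | 3.09 | 970 | 1.76 | 73.5% | 74.2% | 77.3-82.5% |
| 0.10 | 5.19 | 579 | 2.28 | 61.1% | 61.5% | 76.5-83.2% |

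In absolute terms, the half-width at an 80% rate goes from about 1.4 points to 1.7, 2.6 and 3.3 points for ICC 0.01, 0.05 and 0.10.

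**Step 4, unequal sites.** With coefficient of variation CV of site size, DE = 1 + ((1 + CV^2) x m - 1) x ICC. At CV 0.5 the width factors for ICC 0.01, 0.05 and 0.10 are 1.24, 1.90 and 2.50. At CV 1.0 they are 1.36, 2.29 and 3.08.

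**Step 5, denominator.** Section 8.3.1.4 excludes patients from the efficacy set, so the real denominator will be below 3,000. If the number of sites stays the same, m falls and the width factor shrinks somewhat, while the interval before adjustment becomes wider. The direction of the problem does not change.

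**The case against.** The strongest reply is that the size of the problem is assumed. The protocol gives no ICC, and at 0.001 the exact interval is practically correct. This stands, and makes the conclusion conditional. The outcome definition does give a reason to expect some positive correlation, and with 43 patients per site even an ICC of 0.01 doubles the nominal 5% non-coverage to about 10%.

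A second reply is that the design effect treats sites as a sample from a wider population, whereas section 8.2.1 selects sites on qualification criteria. The protocol does not say which population of sites the interval describes. But section 7 speaks of Korean patients in routine practice, so inference beyond the participating sites is the natural reading.

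A third reply is that nothing depends on a point or two of width: this is descriptive surveillance without a success threshold, and the point estimate is unaffected. That limits the weight of the point but does not make the stated 95% correct.

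A reader might go further and infer that every interval, test and regression in the plan is wrong. The document does not support this:

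- The method for adverse-event intervals and the variance estimator for the logistic regressions are left open. A statistical analysis plan could handle clustering there without contradicting the protocol.
- HbA1c, FPG, body weight and blood pressure are measured, so the argument about differing raters does not carry over to the paired t-tests.
- The comparisons in sections 8.7.2 and 8.7.3 use the characteristics listed in section 8.7.1. These are patient-level, and site or hospital type is not among them. For factors that vary within sites, ignoring clustering need not understate standard errors, so it is not shown that site-level factors would appear significant too often.

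**Conclusion.** The point holds for one method that the protocol fixes: the exact 95% CI for the effectiveness rate. As ordinarily calculated it ignores the site structure of a physician-rated outcome, and it is too narrow if ratings correlate within site. The loss ranges from negligible at ICC 0.001 to a factor of 2.28 at ICC 0.10 under equal site sizes, and is larger when sites are unequal. These figures rest on an assumed ICC, about 70 sites and the full 3,000 patients. This is a matter of stated precision: no bias in the effectiveness rate is shown, and no general failure of the plan's other analyses.

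**What to change.** In section 8.7.3, keep the effectiveness rate as it is and keep the exact 95% CI as the regulatory-format figure. Add a site-clustered 95% CI for the same rate, from GEE or a cluster-robust variance with site as cluster, or from a model with a random site effect. Say that this interval is the one to be interpreted, and report the estimated ICC.

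As an option, use the same clustered variance for the overall adverse event and adverse drug reaction incidence intervals and for the logistic regressions. The protocol leaves those details open, so this would be an improvement and not the correction of an error.

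Hospital and physician are already recorded (sections 8.2.3.2 and 8.3.4.5), so no new data, visits or patients are needed. The cost is a change of wording, slightly more analysis work and a somewhat wider reported interval.
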